4.1.4.5 Precautions and surveillance for procedural risks from intratumoural application

Needle insertion into a tumour lesion is associated with procedural risks known from diagnostic biopsy, e.g. infection, bleeding, injury to tissues in the needle track (e.g. nerves, vessels, organs), adverse reactions to local anesthesia if used.

BI 1387446 may only be administered by a physician who is experienced in diagnostic biopsy or intratumoural injection of immunotherapy drugs (physician, radiologist/interventional radiologist, or surgeon).

In case patient develops symptoms potentially indicating local complications, adequate surveillance and additional diagnostic measures need to be implemented as medically appropriate. A decline in Hgb by ≥ 2.0 g/dL (≥ 20 g/L, ≥ 1.24 mmol/L) must result in prolongation of surveillance by at least 4h including repetition of all assessments as per [Table 4.1.4.5: 1](#). Imaging should be performed as medically indicated for diagnosis of a bleed.

Table 4.1.4.5: 1 Duration of in-hospital patient surveillance needs to be adapted for procedural risks

Lesion location	Minimum duration of surveillance	Mandatory assessments
Superficial lesion	30 minutes	vital signs (depending on surveillance period, at least at 30 +/- 15 mins or 60 +/- 15 mins) visual inspection of injection site

In case longer surveillance is mandated on selected visits for other reasons, e.g. risk mitigation of cytokine release syndrome ([Section 4.1.4.6](#)), the longest duration as defined per protocol at a given timepoint will apply.

4.1.4.6 Cytokine release syndrome

Patients will be closely monitored for CRS and, in case of suspected or confirmed CRS, have to receive appropriate and immediate treatment. All trial sites will have emergency resuscitation services and access to intensive care available.

Mandatory surveillance for CRS

- Patients will remain under surveillance for 24 hours after the first administration of BI 1387446 (STING agonist) on Cycle 1 Day 1.
- Patients will remain under surveillance for at least 8 hours after the second and third administration of BI 1387446 on Cycle 1 [REDACTED]
- Patients will remain under surveillance for at least 8 hours on Cycle 2 Day 1.
- Patient will remain under surveillance for at least 8 hours in Cycle 5 Day 1 of Arms A and B.

- Patient surveillance may be shortened on subsequent administrations as medically appropriate, considering the minimum duration as defined in [Section 4.1.4.5](#), provided that no cytokine release syndrome was observed in the previous administration.
- In case a patient suffered from cytokine related symptoms at the previous BI 1387446 injection, the surveillance at the subsequent administration needs to be prolonged to at least 8 hours.
- Patients requiring steroids as premedication or requiring medication for symptoms of any kind (including any signs/symptoms concerning CRS) for any reason during the CRS surveillance periods will stay for observation and continue to be monitored for CRS for at least 24 hours after administration of BI 1387446

Monitoring of asymptomatic patients will include measurement of body temperature, heart rate, and blood pressure, at least every 2 hours. Parameters have to be captured in CRF. Those parameters will not only be used to capture the symptoms of CRS, but also be evaluated for signs of cardiac insufficiency. If more frequent assessments are chosen due to clinical symptoms, a representative selection of these additional assessments need to be captured in the CRF as well. Patients will be assessed for signs or symptoms of CRS (e.g. fever, hypotension, tachycardia, hypoxia, nausea, fatigue, headache, myalgias, and malaise).

Patients will be informed about possible signs and symptoms of CRS, and the need to immediately contact or present to the investigational site if symptoms occur after discharge, or in case of urgency to another, closer hospital.

CRS grading should be performed according to American Society for Blood and Marrow Transplantation (ASBMT) consensus grading [[R19-0309](#)], organ toxicities in the context of CRS should be reported according to Common Terminology Criteria for Adverse Events (CTCAE) v5.0. AEs of CRS Grade ≥ 2 are defined as AESIs.

Treatment of CRS should be based on published recommendations and guidelines [[R19-0310](#), [R19-0311](#)], the recommendations for treatment of CRS in [Appendix 10.2](#) should be considered by the investigator as guidance. In general, in case more than symptomatic treatment is required, corticosteroids should be administered first. IL-6 targeting drugs should be used only once appropriate doses of corticosteroids did not result in adequate improvement or resolution. Pre-emptive administration of anti-IL6-therapy, e.g. use of tocilizumab or siltuximab prior to BI 1387446 injection or immediately thereafter without presence of clinical symptoms of CRS, is not permitted.

In patients with clinically manifested CRS, it is recommended to measure cytokines in the local laboratory at onset of symptoms, approximately 24 hours, and 48 hours thereafter or upon discharge from hospitalization (whichever occurs earlier).

A patient with CRS grade 1 or 2 may be re-exposed to BI 1387446 and ezabenlimab (BI 754091) at the subsequent planned administration timepoint provided that all symptoms have completely resolved for at least 48 hours.

Following a CRS grade 3 or 4, patients must not be re-exposed to the drug which is considered associated with the event. In case of uncertain causality assessment, both trial

drugs must be permanently discontinued. For details on management of trial drugs refer to [Appendix 10.2](#).

4.1.4.7 Management of immune-related AEs

Immune related AEs are expected with the use of ezabenlimab (BI 754091) and/or BI 1387446, and need to be documented and managed according to [Appendix 10.1](#) and published guidelines [[P19-00269](#)].

4.1.5 Blinding and procedures for unblinding

4.1.5.1 Blinding

This trial will be conducted as an open-label fashion.

4.1.5.2 Unblinding and breaking the code

Not applicable.

4.1.6 Packaging, labelling, and re-supply

The investigational medicinal products will be provided by BI or a designated CRO. They will be packaged and labelled in accordance with the principles of Good Manufacturing Practice (GMP). Re-supply to the sites will be managed via an IRT system, which will also monitor expiry dates of supplies available at the sites.

For details of packaging and the description of the label, refer to the ISF.

4.1.7 Storage conditions

Drug supplies will be kept in their original packaging and in a secure limited access storage area according to the recommended storage conditions on the medication label. A temperature log must be maintained for documentation.

If the storage conditions are found to be outside the specified range, the Clinical Trial Manager (as provided in the list of contacts) must be contacted immediately.

4.1.8 Drug accountability

The Investigator or designee will receive the investigational drugs delivered by the sponsor when the following requirements are fulfilled:

- Approval of the clinical trial protocol by the IRB / ethics committee,
- Availability of a signed and dated clinical trial contract between the sponsor and the investigational site,
- Approval/notification of the regulatory authority, e.g. competent authority (CA),
- Availability of the curriculum vitae of the Principal Investigator,
- Availability of a signed and dated clinical trial protocol,
- Availability of the proof of a medical license for the Principal Investigator,

- Availability of FDA Form 1572 (if applicable).

Investigational drugs are not allowed to be used outside the context of this protocol. They must not be forwarded to other Investigators or clinics.

The Investigator or designee must maintain records of the product's delivery to the trial site, the inventory at the site, the use by each patient, and the return to the sponsor or warehouse / drug distribution centre or alternative disposal of unused products. If applicable, the sponsor or warehouse / drug distribution centre will maintain records of the disposal.

These records will include dates, quantities, batch / serial numbers, expiry ('use- by') dates, and the unique code numbers assigned to the investigational medicinal product and trial patients. The Investigator or designee will maintain records that document adequately that the patients were provided the specified doses and reconcile all investigational medicinal products received from the sponsor. Unused and partially used trial drug will be destroyed on site according to local site procedure after relevant reconciliations have been completed.

4.2 OTHER TREATMENTS, EMERGENCY PROCEDURES, RESTRICTIONS

4.2.1 Other treatments and emergency procedures

There are no special emergency procedures to be followed.

4.2.2 Restrictions

4.2.2.1 Restrictions regarding concomitant treatment

Anticancer therapy

No other investigational therapy or anticancer agent should be given to patients. If such agents are required for a patient, then the patient must first be withdrawn from the trial.

Immunosuppressive medications

Immunosuppressive medications including, but not limited to systemic corticosteroids at doses exceeding 10 mg/day of prednisone or equivalent, methotrexate, azathioprine, and tumour necrosis factor-alpha blockers are prohibited. Use of immunosuppressive medications for the management of investigational product-related AEs or in patients with contrast allergies is acceptable, and does not necessarily warrant immediate treatment discontinuation. In addition, use of inhaled, topical, intranasal corticosteroids or local steroid injections (e.g. intra-articular injection) is permitted. Temporary uses of corticosteroids for concurrent illnesses (e.g. food allergies, computed tomography (CT) scan contrast hypersensitivity) are acceptable upon discussion with the Sponsor.

For the treatment of CRS, supportive therapy including steroids, interleukin 6 receptor (IL6R) antagonists and IL6 antagonists may be used as clinically indicated.

Vaccines

In Arm A, live attenuated vaccines are prohibited during the trial through 30 days after the last dose of BI 1387446. In Arm B, the use of live attenuated viruses has to be delayed until 70 days after the last dose of ezabenlimab (BI 754091) or 30 days after the last dose of BI 1387446, whichever comes later.

The decision on COVID-19 vaccination of a BI study patient must be taken based on an individual Benefit-Risk Assessment by the investigator after thorough discussion with the patient. This assessment should consider the approved labels of the respective vaccine as well as the provisions given in the Clinical Trial Protocol. Furthermore, there should be a time window of at least 3 days between administration of the vaccine and study medication. COVID-19 vaccination or BI 1387446 may be postponed considering the patients individual risk. COVID-19 vaccination should be considered as concomitant medication and reported as such in the CRF.

Considering the mechanism of action of activation of the STING pathway and PD-1 receptor blockade, attenuation of vaccine-induced protective immunity by BI 1387446 and/or BI 754091, respectively, is not assumed.

The package insert for approved COVID-19 vaccinations should be carefully reviewed for local guidance considering acute moderate/severe febrile illness, and the risk of an anaphylactic reaction to the vaccine. A diminished response to the vaccine needs to be considered for immunocompromised conditions which may be observed in patients with advanced or metastatic solid tumour after prior anti-cancer therapies.

It is important to encourage a patient to continue taking precautions such as wearing a mask, maintaining social distancing and washing hands frequently, even after a patient receives a COVID-19 vaccine. These precautions will be necessary until public health experts advise otherwise.

Herbal medications

Herbal preparations/medications are not allowed throughout the trial unless agreed to by the Principal Investigator. These herbal medications include, but are not limited to: St. John's wort, kava, ephedra (ma huang), gingko biloba, dehydroepiandrosterone (DHEA), yohimbe, saw palmetto, and ginseng. If instructed by the Principal Investigator, patients should stop using these herbal medications 7 days prior to first dose of study treatment.

Palliative radiotherapy

For symptom control, palliative radiotherapy of a single lesion is permitted in the dose escalation part of the trial, except during the first cycle as it could interfere with the DLT evaluation for MTD determination. Palliative radiotherapy is allowed only for lesions which are not previously injected with BI 1387446, provided that the reason for radiotherapy does not reflect PD and does not interfere with response assessment. Lesions that have been exposed to radiotherapy are no longer evaluable, and may not be included in the imaging based response assessment of target/ non-target lesions and the overall assessment. The

Sponsor should be informed prior to the administration of palliative radiotherapy, except for emergency situations.

IL-6 antagonists

In case tocilizumab or other IL-6 antagonists are required for management of severe adverse events, BI 1387446 and ezabenlimab (BI 754091) have to be permanently discontinued.

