Grade 2	Fever >38°C with either hypotension not requiring vasopressors and/or hypoxia requiring low-flow nasal cannula or blow-by	
 - manage fever and constitutional symptoms as in grade 1 - supplemental oxygen as needed - IV fluid bolus of normal saline (500-1000 mL) - consider second IV fluid bolus if systolic blood pressure remains <90 mmHg - dexamethasone 10 mg IV every 6h - if hypotension persists after 2 fluid boluses and dexamethasone, start vasopressors and consider transfer to ICU - anti-IL6-therapy, e.g. tocilizumab or siltuximab, may be considered - symptomatic management of organ toxicities as per standard guidelines 	
 - stop administration of BI 1387446 and ezabenlimab (BI 754091) if not fully administered - continue treatment with the subsequent administration of BI 1387446 and ezabenlimab (BI 754091) provided that all symptoms have completely resolved for at least 48 hours - delay/skip the subsequent administration if needed to ensure that all symptoms have completely resolved for at least 48 hours - at the subsequent administration of the respective drug, patients should be under close surveillance of appropriate duration
Grade 3	Fever >38°C with either hypotension requiring one vasopressor with or without vasopressin and/or hypoxia requiring high-flow nasal cannula, facemask, non-rebreather mask or Venturi mask	
 - IV fluid boluses and vasopressors as needed - transfer to ICU, initiate hemodynamic monitoring - dexamethasone 10 mg IV every 6h, if refractory increase to 20 mg IV every 6h - supplemental oxygen as needed - manage fever and constitutional symptoms as indicated for grade 1 - anti-IL6-therapy, e.g. tocilizumab or siltuximab, may be considered - symptomatic management of organ toxicities as per standard guidelines 	
 - stop administration of BI 1387446 and ezabenlimab (BI 754091) if not fully administered - if CRS is considered unequivocally related to BI 1387446: do not re-expose the patient to BI 1387446, ezabenlimab (BI 754091) may be continued as per protocol once CRS has completely resolved for at least 7 days - if CRS is unequivocally related to ezabenlimab (BI 754091): permanently discontinue ezabenlimab (BI 754091) - If there is uncertainty about causality assessment: permanently discontinue BI 1387446 and ezabenlimab (BI 754091) -

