Table 10.2: 1 CRS grading, treatment and management of trial drugs (cont.)

Grade	Definition of grade	Recommendation for treatment of CRS	Management of trial drugs
Grade 4	Fever >38°C with either hypotension requiring multiple vasopressors (excl. vasopressin) and/or hypoxia requiring positive pressure, e.g. continuous positive airway pressure (CPAP), bilevel positive airway pressure (BiPAP), intubation and mechanical ventilation	
- ICU transfer, IV fluids, vasopressors and hemodynamic monitoring as indicated for grade 3- manage fever and constitutional symptoms as indicated for grade 1- methylprednisolone 1 g/day IV- respiratory support including mechanical ventilation- anti-IL6-therapy, e.g. tocilizumab or siltuximab, may be considered- symptomatic management of organ toxicities as per standard guidelines	
- same as for grade 3

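### The anti-IL-6 stop in Protocol 4.2.2.1 is absent from the CRS guidance that sites are told to use, which lets ezabenlimab continue after some grade 3–4 CRS and leaves grade 2 unsettled

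*Protocol*

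**What the plan says.** The last rule of Protocol 4.2.2.1 is mandatory: if "tocilizumab or other IL-6 antagonists are required for management of severe adverse events, BI 1387446 and ezabenlimab (BI 754091) have to be permanently discontinued". It has no causality exception and names no grade. Section 3.3.4.1 separately gives CRS of grade 3 or higher as an example of an event requiring permanent discontinuation of trial drugs.

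Section 4.1.4.6 allows IL-6-targeting drugs once corticosteroids have proved inadequate. It permits re-exposure to both drugs after grade 1–2 CRS. After grade 3–4 it bars only the drug held responsible, or both if causality is uncertain. For the details of trial-drug management it sends the reader to Appendix 10.2.

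Table 10.2:1 in that appendix lists "anti-IL6-therapy, e.g. tocilizumab or siltuximab, may be considered" in the grade 2, 3 and 4 rows. Its trial-drug column reads as follows:

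- Grade 2: "continue treatment with the subsequent administration of BI 1387446 and ezabenlimab (BI 754091) provided that all symptoms have completely resolved" for at least 48 hours.
- Grade 3, unequivocally due to BI 1387446: BI 1387446 is not given again, but "ezabenlimab (BI 754091) may be continued as per protocol once CRS has completely resolved for at least 7 days".
- Grade 3, unequivocally due to ezabenlimab: only ezabenlimab is named for discontinuation.
- Grade 3, causality uncertain: both drugs stop.
- Grade 4: "same as for grade 3".

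Neither 4.1.4.6 nor the table mentions the 4.2.2.1 rule.

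**The concern.** A site managing CRS is directed to Table 10.2:1, not to the concomitant-medication section. A site that follows the table could give an IL-6 antagonist and then continue a drug that 4.2.2.1 says must stop.

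The rule has a plausible reason behind it. Section 1.2.1 reports that in monkeys tocilizumab given 24 hours before BI 1387446 markedly raised cytokine levels compared with BI 1387446 alone, while tocilizumab given 6 hours afterwards had no relevant effect. The possible hazard is therefore the next BI 1387446 injection after an IL-6 antagonist. Section 4.1.4.6 already forbids pre-emptive anti-IL-6 therapy.

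There is also a link to the primary endpoint. Whether a Cycle 1 patient is stopped or continues can decide whether that patient enters the MTD set.

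**Working it through.** The plan gives no figure to reproduce. The check sets the sections side by side for a patient who has received anti-IL-6 therapy.

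| Case | 4.1.4.6 and Table 10.2:1 | 4.2.2.1 | 3.3.4.1 | Result |
|---|---|---|---|---|
| Grade 3–4, Arm B, unequivocally BI 1387446 | Stop BI 1387446; ezabenlimab may continue | Stop both | Trial drugs stop | Inconsistent |
| Grade 3–4, Arm B, unequivocally ezabenlimab | Stop ezabenlimab; BI 1387446 left open (4.1.4.3 allows the other drug) | Stop both | Trial drugs stop | Inconsistent, but Section 1.2.3 makes this attribution unlikely |
| Grade 3–4, Arm B, uncertain causality | Stop both | Stop both | Trial drugs stop | Consistent |
| Grade 2, either arm | Both may resume after 48 symptom-free hours | Stop both if *severe* | Not listed | Undetermined |

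*Without anti-IL-6.* The rule in 4.2.2.1 then does not apply, but 3.3.4.1 still points to stopping while the table allows ezabenlimab to continue in the first case. Repeating the 4.2.2.1 rule in the table does not settle that.

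*The word severe.* Section 5.2.7.1.5 grades adverse events by CTCAE v5.0, and 4.1.4.6 grades CRS by ASBMT. Neither scale is mapped to the word, so the text does not say whether grade 2 CRS is covered.

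*How narrow grade 2 is.* Corticosteroids come first. Then "if hypotension persists after 2 fluid boluses and dexamethasone, start vasopressors and consider transfer to ICU", and a vasopressor requirement makes the event grade 3. What remains is mainly low-flow hypoxia that does not respond to steroids, or anti-IL-6 given before vasopressors.

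*Time to the next BI 1387446 injection under the grade 2 row.*

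- Lower bound: anti-IL-6 without CRS symptoms is not permitted, and symptoms must be gone for 48 hours, so at least 48/24 = 2 days.
- Cycles 1–3: three visits per 3-week cycle (Flow Chart, Section 6.1), weekly administration (5.3.1), and a fourth injection that opens Cycle 2 (SAP 5.1), so up to 21/3 = 7 days.
- From Cycle 4: one visit per 3-week cycle, so up to 21 days.

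These figures assume anti-IL-6 is given no earlier than the day of the last injection and that the next injection is neither delayed nor skipped. The exact treatment days are redacted. The monkey interval was 24 hours, or 1 day. The documents contain no data at 2 to 21 days, so the calculation shows only that re-dosing falls outside the tested interval.

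*MTD set.* The CRS-specific DLT criterion begins at grade 3 (4.1.4.4). Take a Cycle 1 patient with grade 2 CRS treated with anti-IL-6 who meets no other DLT criterion:

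- Stopped before completing the required injections: non-evaluable under 3.3.4.4 and SAP 6.4, excluded under SAP 6.3, and normally replaced.
- Continues without a missed dose and has the Cycle 2 Day 1 echocardiogram or MUGA scan: counted as evaluable without a DLT.

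**The case against.** The strongest reply is that this is a missing cross-reference and not a clash of obligations. The table says ezabenlimab *may* continue, and *as per protocol*, which can be read as subject to 4.2.2.1. Appendix 10.2 describes its recommendations as guidance. Stopping both drugs satisfies every section. All of that is right, and it lowers the weight of the point. It does not remove it: no order of precedence is stated, and the body text of 4.1.4.6 also bars only the associated drug after grade 3–4.

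The plural *trial drugs* in 3.3.4.1 may also be loose. The same list includes grade 3 infusion reactions to ezabenlimab, for which 4.1.4.3 stops only ezabenlimab. That is a further reason to clarify 3.3.4.1.

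At grade 2, *severe* can naturally be read to exclude the event. Section 4.2.2.1 itself says that immunosuppressives for product-related events do not necessarily require immediate discontinuation. A deliberately graded design is therefore possible. This stands, and it is why grade 2 is treated here as an ambiguity.

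Finally, SAP Section 4 says development has been terminated. However, Protocol 3.3.5 lets consented patients continue their treatment plan if development ends, and neither document shows that dosing has stopped. If nobody remains on treatment, the urgency goes but the inconsistency remains.

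**Conclusion.** The inconsistency is real and of minor to moderate severity. For grade 3–4 CRS in Arm B that is treated with anti-IL-6 and attributed unequivocally to BI 1387446, the protocol permits in one place what it prohibits in another. Section 3.3.4.1 disagrees with the table even without anti-IL-6. For grade 2, in both arms, the protocol does not say which instruction applies.

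The number affected cannot be estimated. The documents give no frequency of CRS or of anti-IL-6 use in this trial, and Section 1.4.2 notes that no CRS with hypotension or hypoxia was reported with other STING agonists. Arm B is planned at about 44 patients plus cross-overs; that is the size of the arm, not a count of affected patients.

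A reader might infer three stronger claims that the documents do not support:

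- *That continuing ezabenlimab after anti-IL-6 is shown to be harmful.* The monkey finding concerns BI 1387446 given after tocilizumab, and Section 1.2.3 says ezabenlimab does not cause cytokine release.
- *That the grade 2 row contradicts 4.2.2.1.* It does so only if *severe* includes grade 2, which is not stated.
- *That BI 1387446 must be barred after anti-IL-6 at grade 2.* The risk at the actual re-dosing intervals is unknown, and such a bar would be a new rule with a cost to MTD evaluability.

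**What to change.** 1. In the grade 3 and grade 4 rows of Table 10.2:1, and in the grade 3–4 paragraph of 4.1.4.6, add: *if anti-IL-6 therapy was given, permanently discontinue BI 1387446 and ezabenlimab (Section 4.2.2.1)*.
2. Align 3.3.4.1 with the table on whether ezabenlimab may continue after grade 3–4 CRS when no anti-IL-6 was given.
3. In 4.2.2.1, define *severe* by ASBMT grade for CRS, so that it is clear whether grade 2 treated with anti-IL-6 is covered. Carry the decision into the grade 2 row and the grade 1–2 re-exposure sentence of 4.1.4.6. The sponsor should decide this in light of the monkey finding.

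The cost is a few sentences of protocol text and a letter to sites. If grade 2 is covered, some patients lose further treatment. Those stopped in Cycle 1 before completing the required injections and without a DLT leave the MTD set and are normally replaced, which takes cases of treatment-related toxicity out of the dose-toxicity model. That should be weighed openly when the grade is chosen. No new data and no SAP change are needed.
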